4.1. Protocol Deviations

Important protocol deviations (including deviations related to study inclusion/exclusion criteria, conduct of the trial, patient management or patient assessment) will be summarised and listed.

Protocol deviations will be tracked by the study team throughout the conduct of the study in accordance with the Protocol Deviation Management Plan.

- Data will be reviewed prior to the DBF (database freeze) milestone for each study part (Part A and Part B) to ensure all important deviations are captured and categorised on the protocol deviations dataset.
- This dataset will be the basis for the listings of protocol deviations.

A separate listing of all inclusion/exclusion criteria deviations will also be provided. This listing will be based on data as recorded on the inclusion/exclusion page of the eCRF.

5. CONSIDERATIONS FOR DATA ANALYSES AND DATA HANDLING CONVENTIONS

5.1. Other Considerations for Data Analyses and Data Handling Conventions

The table below provides an overview of appendices within the RAP for outlining general considerations for data analyses and data handling conventions:

Section	Component
12.3	Appendix 3: Study Phases and Treatment Emergent Adverse Events
12.4	Appendix 4: Data Display Standards & Handling Conventions
12.5	Appendix 5: Derived and Transformed Data
12.6	Appendix 6: Reporting Standards for Missing Data
12.7	Appendix 7: Values of Potential Clinical Importance

6. STUDY POPULATION ANALYSES

6.1. Overview of Planned Study Population Analyses

The study population analyses will be based on the “Safety” population, unless otherwise specified. Screen failures will be summarised or listed based on the “Screened” population.

Table 1 provides an overview of the planned study population analyses, with full details of data displays being presented in Appendix 9: List of Data Displays.

Table 1 Overview of Planned Study Population Analyses

Display Type	Data Displays Generated	
	Table	Listing
Subject Disposition		
Subject Disposition	Y	
Reasons for Screening Failures	Y	Y
Reasons for Discontinuation of Study Treatment	Y	Y
Number of Participant	Y	
Reasons for Withdrawals		Y
Study Population		
Study Populations	Y	
Participants Excluded from any Population		Y
Protocol Deviations		
Important Protocol Deviations	Y	Y
Inclusion and Exclusion Criteria Deviations		Y
Demography		
Demography Characteristics	Y	Y
Age Ranges	Y	
Race and Racial Combinations	Y	Y
Concomitant Medications		
Concomitant Medication	Y	Y
Past Medical Conditions	Y	Y
Current Medical Conditions	Y	Y
Exposure		
Exposure to Total anti-SAP mAb*	Y	Y
Exposure to GSK2315698	Y	Y

NOTES :

Y = Yes display generated.

*Total Mass Dose (TMD) of anti-SAP mAb = unlabelled anti-SAP mAb + ⁸⁹Zr-GSK2398852.

7. PRIMARY STATISTICAL ANALYSES

7.1. Primary Analyses

7.1.1. Endpoint / Variables

- Standardized Uptake Values (SUV) [i.e. Radioactivity concentrations] in focal anatomical locations within the heart, as well as SUV of the whole heart at different time points after ⁸⁹Zr-GSK2398852 administration and at different anti-SAP mAb TMDs.

7.1.2. Summary Measure

Data will be listed according to the GSK reporting standards, where applicable. All PET imaging parameters will be listed. Individual subject plots for the PET imaging parameters will also be produced.

Note that, in any one subject in Part A, where the radiolabel PK and cardiac SUV profile of ⁸⁹Zr-GSK2398852 is consistent with myocardial uptake during either the 1st or 2nd dosing session (i.e. cardiac / plasma SUV ratio ≥ 0.5), the reproducibility of this specific unlabelled anti-SAP mAb dose in enabling myocardial uptake of ⁸⁹Zr-GSK2398852 may be evaluated by treating further subjects with the same unlabelled anti-SAP mAb mass dose.

7.1.3. Population of Interest

The analyses in this section will be based on the “All Treated” population, unless otherwise specified.

7.1.4. Statistical Analyses / Methods

Table 2 provides an overview of the planned primary analyses, with full details of data displays being presented in Appendix 9: List of Data Displays which will be based on GSK data standards and statistical principles.

Table 2 Overview of Planned Primary Analyses

Endpoint / Parameter / Display Type	Absolute			
	Summary		Individual	
	T	F	F	L
PET (cardiac images)				
For the whole heart: SUV _{mean} and volume For each cardiac focal anatomical location: SUV _{peak} over the entire 20-minute scan period, and volume			Y ¹	Y

NOTES :

[1] Figures will be restricted to SUV_{mean} values and SUV_{peak} values over the entire 20-minute scan period.

T = Table, F = Figure, L = Listing, Y = Yes display generated.

7.2. Secondary Analyses

7.2.1. Endpoint / Variables

Focal and total radioactivity uptake (including, but not limited to SUV) in different tissues (including potentially at those peripheral tissue sites where transthyretin amyloidosis (TTR) amyloid deposition can be clinically occult) at different time points and after different TMDs.

7.2.2. Summary Measure

Data will be listed according to the GSK reporting standards, where applicable. All PET imaging parameters will be listed

7.2.3. Population of Interest

The analyses in this section will be based on the “All Treated” population, unless otherwise specified.

7.2.4. Statistical Analyses / Methods

[Table 3](#) provides an overview of the planned secondary analyses, with full details of data displays being presented in [Appendix 9: List of Data Displays](#) which will be based on GSK data standards and statistical principles.

Table 3 Overview of Planned Secondary Analyses

Endpoint / Parameter / Display Type	Absolute			
	Summary		Individual	
	T	F	F	L
PET (non-cardiac images)				
For each organ/ tissue: SUVmean and volume			Y ¹	Y

NOTES :

[1] Figure will be restricted to SUVmean values.

T = Table, F = Figure, L = Listing, Y = Yes display generated.

8. SAFETY ANALYSES

The safety analyses will be based on the Safety population, unless otherwise specified. Analyses detailed in this section will be performed on data from each study part separately.

[Table 4](#) provides an overview of the planned safety analyses, with full details of data displays being presented in [Appendix 9: List of Data Displays](#).

Table 4 Overview of Planned Adverse Events Analyses

Endpoint / Parameter / Display Type	Absolute	
	Summary	Individual
	T	L
Adverse Events (AEs)		
All AEs by System Organ Class (SOC) and Preferred Term (PT)	Y	Y
Common (≥5%) Adverse Events by Overall Frequency	Y	
Common (≥5%) Grade 2-4 Adverse Events by Overall Frequency	Y	
Drug-Related AEs by SOC and PT	Y	
Common (≥5%) Non-Serious AEs by SOC and PT (Subjects & No. of Occurrences)	Y	
Common (≥5%) Drug Related Grade 2-4 Adverse Events by SOC and PT	Y	
Subject Numbers for Individual AEs		Y
Relationship Between Adverse Event System Organ Classes, Preferred Terms, and Verbatim Text		Y
Serious and Other Significant AEs		
Fatal Serious AEs		Y
Non-Fatal Serious AEs		Y
Reasons for Considering as a Serious AE		Y
Serious AEs by SOC and PT (Subjects & No. of Occurrences)	Y	
AEs Related to Treatments other than the Study Drug		Y
AEs Leading to Withdrawal from Study / Permanent Discontinuation of Study Treatment by SOC and PT	Y	Y
Temporally-Associated, Potential mAb-Related Infusion Events ¹		Y
Anti-SAP mAb Infusion Related Reactions ¹		Y

NOTES:

- T = Table, L = Listings, Y = Yes display generated, SOC = System Organ Class, PT = Preferred Term.
- Summary = Represents Tables related to any summaries (i.e. descriptive statistics) of the observed raw data.
- Individual = Represents Listings related to any displays of individual subject observed raw data.
- [1] Further details provided in Section [8.2](#)

8.1. Adverse Events Analyses

Adverse events analyses including the analysis of adverse events (AEs), Serious (SAEs) and other significant AEs will be based on GSK Core Data Standards. The details of the planned displays are provided in [Appendix 9: List of Data Displays](#). Tables will present AEs in the treatment phase. Listings will present all AEs

8.2. Adverse Events of Special Interest (AESI) Analyses

The following categories of AESIs associated with GSK2398852 have been identified to date:

- Rash, Rash AESI will be identified based on the eCRF rash question and flagged in the general AE listing.
- Anti-SAP mAb Infusion-related reaction (IRR).

The identification of anti-SAP mAb IRR will follow a two-step process.

Step 1

A listing of temporally-associated, potential mAb-related infusion events (TPMI) will be produced.

TPMIs will only include AEs that correspond to the following list of preferred terms:

- “Headache”, “Flushing”, “Feeling hot”, “Feeling cold”, “Chest discomfort”, “Chills”, “Face oedema”, “Oedema peripheral”, “Orbital oedema”, “Nausea”, “Vomiting”, “Diarrhoea”, “Fatigue”, “Tachycardia”, “Presyncope”, “Infusion related reaction”.

In addition, TPMIs will be restricted to AEs that occurred during the mAb infusion or within 24 hours of the end of the mAb infusion. If the AE start time is missing, the AE will be included as TPMI if the AE start date is the same as the mAb infusion start date or end date (either dates if not the same), or if the AE start date is the next day after the end of the mAb infusion.

Step 2

This initial selection of AEs will be manually reviewed by the clinical team to identify the subset of TPMI events that qualify as IRR.

As a result, a listing of IRR (only including AEs flagged by this clinical review) will be displayed. If there is no AE identified as IRR as part of the clinical review, this listing will not be produced.

The details of the planned displays are provided in [Appendix 9: List of Data Displays](#).

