#### **3.4.1.2. Potential for mAb Infusion-Related Reactions (IRR)**

Most subjects receiving more than 200 mg of anti-SAP mAb in the FIH study experienced infusion-related reactions varying in type and severity, which included headache; flushing; hot or cold feelings; chest discomfort; chills; facial, orbital and peripheral oedema; nausea; vomiting; diarrhoea; fatigue; tachycardia; pre-syncope. These symptoms were reduced by slowing or temporarily interrupting the infusion and were further mitigated by pre-medication with hydrocortisone and chlorphenamine.

See Section 3.4.3 for risk mitigation strategy.

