**Table 6 Proposed Duration and Timing of anti-SAP mAb and Zr-GSK2398852 administration**

Total Mass Doses of anti-SAP mAb	Proposed Duration of Unlabelled anti-SAP mAb Infusions	Planned Timing of  Zr-GSK2398852 Administration in Relation to Unlabelled anti-SAP mAb Infusion 
80 – 200 mg	1 Hour	Simultaneous administration: Both infusions administered over 1 hour & finishing at approximately the same time 
200 mg < Total Mass Dose ≤500 mg	6 Hours	Co-administration:  Zr-GSK2398852 administered over 1 hour, commencing any time after start of unlabelled anti-SAP mAb, including after its completion

If a subject experiences infusion reaction, dosing may be paused and resumed at investigator discretion.

Unlabelled anti-SAP mAb and Zr-GSK2398852 will be administered via two separate peripheral venous lines

After the first subject, there is an option (based on emerging data) that administration of Zr-GSK2398852 may be initiated at any time during the infusion or after the unlabelled anti-SAP mAb infusion has completed.

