## Recording AE and SAE

### AE and SAE Recording

- When an AE/SAE occurs, it is the responsibility of the investigator to review all documentation (e.g., hospital progress notes, laboratory, and diagnostics reports) related to the event.
- The investigator will then record all relevant AE/SAE information in the CRF.
- It is **not** acceptable for the investigator to send photocopies of the subject's medical records to GlaxoSmithKline (GSK) in lieu of completion of the GSK /AE/SAE CRF page.
- There may be instances when copies of medical records for certain cases are requested by GSK. In this case, all subject identifiers, with the exception of the subject number, will be redacted on the copies of the medical records before submission to GSK.
- The investigator will attempt to establish a diagnosis of the event based on signs,

symptoms, and/or other clinical information. Whenever possible, the diagnosis (not the individual signs/symptoms) will be documented as the AE/SAE.

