12.4. Appendix 4: Data Display Standards & Handling Conventions

12.4.1. Baseline Definitions

For all endpoints, the baseline value used for descriptive summaries and listings will be the latest assessment prior to first administration of anti-SAP treatment.

The first administration of anti-SAP treatment will be defined as the first administration of either study drug, i.e. CPHPC or anti-SAP mAb (labelled or unlabelled).

Derivations and Handling of Missing Baseline Data

Definition	Reporting Details
Change from Baseline	= Post-Dose Visit Value – Baseline
Maximum Change from Baseline	= Calculate the change from baseline at each given timepoint after baseline (over treatment sessions and follow up period) and determine the maximum change

NOTES :

- Unless otherwise specified, the baseline definitions specified in Section 12.4.1 will be used for derivations for endpoints / parameters and indicated on summaries and listings.
- Unless otherwise stated, if baseline data is missing no derivation will be performed and will be set to missing.
- The baseline definition will be footnoted on all change from baseline displays.

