22.	Safety	AE8CP	Listing of Adverse Events Related to Treatments other than Study Drug		IA, SAC
Hepatobiliary (Liver)					
23.	Safety	MH2	Listing of Medical Conditions for Participants with Liver Stopping Events		IA, SAC
24.	Safety	SU2	Listing of Substance Use for Participants with Liver Stopping Events		IA, SAC
All Laboratory					

ICH: Listings					
No.	Population	IDSL / Example Shell	Title	Programming Notes	Deliverable [Priority]
25.	Safety	LB5	Listing of All Laboratory Data for Subjects with Any Value of Potential Clinical Concern/Potential Clinical Importance		IA, SAC
26.	Safety	LB5	Listing of Laboratory Values of Potential Clinical Importance		IA, SAC
27.	Safety	LB14	Listing of Laboratory Data with Character Results		IA, SAC
ECG					
28.	Safety	EG3	Listing of All ECG Values for Participants with Any Value of Potential Clinical Importance		IA, SAC
29.	Safety	EG3	Listing of ECG Values of Potential Clinical Importance		IA, SAC
30.	Safety	EG5	Listing of Abnormal ECG Findings		IA, SAC
Vital Signs					
31.	Safety	VS4	Listing of All Vital Signs Data for Participants with Any Value of Potential Clinical Importance		IA, SAC
32.	Safety	VS4	Listing of Vital Signs of Potential Clinical Importance		IA, SAC

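### As printed, the SAP's vital-sign decrease flags do not isolate large falls; separately, the infusion-reaction search is narrower than it needs to be

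*SAP*

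**What the plan says.** **Vital signs.** SAP 12.7.5 sets absolute limits of potential clinical importance: systolic below 90 or above 180 mmHg, diastolic below 30 or above 110 mmHg, heart rate below 35 or above 140 bpm. It also sets limits on change from baseline. The increase rows are greater than 50, 30 and 50. The decrease rows carry the same three numbers with a less-than sign and no minus sign. SAP 12.4.1 defines change from baseline as "Post-Dose Visit Value – Baseline", so a fall is negative. The flags feed Listing 31 (all vital signs for any participant with a flagged value) and Listing 32, titled "Listing of Vital Signs of Potential Clinical Importance".

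**Infusion-related reactions (IRR).** SAP 8.2 works in two steps. Step 1 selects temporally associated potential mAb-related infusion events (TPMI): "TPMIs will only include AEs that correspond to the following list of preferred terms", with onset during the mAb infusion or within 24 hours of its end. In Step 2 the clinical team reviews that list to "identify the subset of TPMI events that qualify as IRR". Listing 21 shows only the events so flagged and is not produced if there are none. Protocol 3.4.1.2 describes the first-in-human experience as "infusion-related reactions varying in type and severity, which included headache" and further symptoms.

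**Grades.** SAP Table 4 plans "Common (≥5%) Grade 2-4 Adverse Events by Overall Frequency". Protocol Appendix 4 rates adverse events (AEs) as mild, moderate or severe. Protocol Table 12 defines Grades 1 to 4 for rash only.

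**The concern.** Vital signs and the incidence and grading of infusion-related reactions are both part of the secondary safety endpoint (SAP 2.3). With six planned completers, safety is judged largely from individual listings, so each listing should contain what its title promises.

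The vital-sign decrease rows do not do this on either literal reading. The infusion-reaction rule is internally consistent, but it turns an illustrative symptom list into an exhaustive one and gives reviewers no way to add to it. If nothing on the closed list is flagged, Listing 21 disappears, and its absence could be taken to mean that no reaction occurred.

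**Working it through.** The SAP gives no figure to reproduce here. The check applies the printed rules to possible values and then compares the passages.

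**1. Decrease rows read as size of fall.** Let B be baseline, x the post-dose value, d the change limit and L the lower absolute limit (all from SAP 12.7.5).

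- The printed rule flags falls with 0 < B - x < d.
- A rule mirroring the increase rows would flag B - x > d.
- The two sets do not overlap.
- A large fall is unflagged when L ≤ x < B - d, which is possible only if B > L + d.

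| Sign | L | d | Baseline above which a large fall can escape | Example baseline | Missed post-dose values (integers) |
|---|---|---|---|---|---|
| Systolic (mmHg) | 90 | 50 | 90 + 50 = 140 | 150 | 90 to 99 |
| Diastolic (mmHg) | 30 | 30 | 30 + 30 = 60 | 80 | 30 to 49 |
| Heart rate (bpm) | 35 | 50 | 35 + 50 = 85 | 100 | 35 to 49 |

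A systolic change from 150 to 95 (a fall of 55) meets no printed rule, while 120 to 115 (a fall of 5) is flagged. From a diastolic baseline of 80, values of 51 to 79 are flagged and 30 to 49 are not.

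**2. Decrease rows read as signed change.** The rule becomes x - B < 50 (or < 30). On a grid of integer changes from -80 to +80 (161 values):

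- Limit 50: -80 to +49 are flagged, 130 of 161. The increase row adds +51 to +80, another 30. Together 160 of 161 are flagged; only +50 is not.
- Limit 30: -80 to +29 are flagged, 110 of 161. The increase row adds +31 to +80, another 50. Again 160 of 161.

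No large fall is missed, but zero change and a rise of 10 are also flagged as decreases.

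**3. Mirrored rule.** Change below -50, -30 and -50 flags 30, 50 and 30 of the 161 grid values for systolic, diastolic and heart rate: falls beyond the limit and nothing else.

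**4. Infusion-reaction terms.** SAP 8.2 lists 16 distinct preferred terms. Protocol 3.4.1.2 names 15 symptoms, counting hot and cold feelings as two and the three oedema sites as three. Fifteen SAP terms match these one to one; the sixteenth is Infusion related reaction. The protocol's list is open and the SAP's is closed. Protocol 3.4.3 includes blood-pressure monitoring among the mitigations for infusion reactions, yet none of the 16 is a blood-pressure term.

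**5. The time window.** SAP 8.2 refers to the mAb infusion in the singular. There are two. For total mass doses above 200 mg, Protocol Table 6 allows the labelled infusion to run for 1 hour, "commencing any time after start of unlabelled anti-SAP mAb, including after its completion". If it follows the unlabelled one, the two possible 24-hour windows end at least 1 hour apart. SAP 12.3.3 specifies labelled or unlabelled mAb when it defines onset day; SAP 8.2 does not.

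**The case against.** **Vital signs.** The rows are labelled as change from baseline, which the SAP defines as signed. A reader might infer that large falls will certainly drop out of Listing 32. The documents do not support that: it follows only from the size-of-fall reading, and on the signed reading the fault is over-flagging. A limit of below -50 is also what a signed definition would naturally produce, so a minus sign may have been lost when the PDF was read, although all three rows show the same pattern. Nor are falls hidden overall. Table 3.22 summarises change from baseline, Figure 3.1 plots every subject, and the Part A interim includes individual profiles of blood pressure and heart rate. This all stands and limits the effect to Listings 31 and 32. It does not make the printed rows usable.

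**Infusion reactions.** A reader might infer that true reactions would be lost from the report, or that the rule is an error. Neither is supported. Protocol Appendix 4 says "Whenever possible, the diagnosis (not the individual signs/symptoms) will be documented as the AE/SAE", and the diagnosis term is on the list. Any other event remains in Listing 13 with its onset day since the session's first mAb dose (SAP 12.3.3). The between-session safety review in Protocol 5.10.1 covers adverse events generally. No infusion-reaction rate is computed, so none can be biased. The two-infusion ambiguity affects mainly the tail of the window. What remains is that a reaction coded only to an unlisted symptom cannot enter Listings 20 or 21, whatever the reviewers think of it.

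**Grades.** A reader might infer that non-rash events cannot enter Tables 3.3 and 3.6. That depends on what the eCRF collects, which the documents do not show.

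**Conclusion.** The vital-sign decrease rows are wrong as printed and should be corrected or confirmed against the source. Neither literal reading isolates large falls. On the size-of-fall reading, omission from Listing 32 is possible only above the baselines of 140 mmHg, 60 mmHg and 85 bpm. The documents give no baseline distribution, so the number of subjects affected cannot be stated. On the signed reading nothing is omitted and the flag carries almost no information.

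The infusion-reaction search is too narrow rather than wrong. Its effect is confined to Listings 20 and 21, and widening it is a cheap improvement.

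The Grade 2-4 item is a query, not a finding.

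The study tests no hypothesis (SAP 2.5), and none of this changes an estimate, an error rate or the sample size.

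**What to change.** 1. **SAP 12.7.5.** Check the source file for a lost minus sign. If the rows are as printed, restate them to mirror the SAP's own increase rows: change from baseline below -50 mmHg (systolic), below -30 mmHg (diastolic), below -50 bpm (heart rate). Listings 31 and 32 then show what their titles say. Cost: three table rows and the matching code.

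2. **SAP 8.2.** Keep the 16 terms as a prompt list. Let the clinical reviewers add any adverse event with onset during either mAb infusion, labelled or unlabelled, or within 24 hours of the end of the later one, and state that window. Cost: a few words, light programming and a slightly longer review list over at most 3 × 2 + 3 = 9 planned dosing sessions (more if subjects are replaced under Protocol 5.7).

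3. **Query.** Ask which scale Grade 2-4 uses in Tables 3.3 and 3.6, and record the answer in the SAP.

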8.3. Clinical Laboratory Analyses

Laboratory evaluations including the analyses of Chemistry laboratory tests, Hematology laboratory tests, Urinalysis, and liver function tests will be based on GSK Core Data Standards.

Table 5 provides an overview of the planned clinical laboratory analyses, with full details of data displays being presented in Appendix 9: List of Data Displays.

Table 5 Overview of Clinical Laboratory Analyses

Endpoint / Parameter/ Display Type	Absolute		
	Summary	Individual	
	T	F	L
Chemistry			
Chemistry Changes from Baseline	Y		
Chemistry Shifts from Baseline Relative to Normal Range	Y		
Hematology			
Hematology Changes from Baseline	Y		
Clinically-Relevant Changes in Haemoglobin	Y		
Hematology Shifts from Baseline Relative to Normal Range	Y		
Urinalysis			
Urinalysis Changes from Baseline	Y		
Urinalysis Parameters Shifts from Baseline Relative to Normal Range	Y		
All Laboratory			
All Laboratory Data for Subjects with any Value of PCI			Y
Laboratory Values of PCI			Y
Laboratory Data with Character Results			Y
Liver Monitoring/Stopping Event Reporting	Y		
Medical Conditions for Participants with Liver Stopping Events			Y
Substance Use for Participants with Liver Stopping Events			Y
Hepatobiliary Laboratory Abnormalities	Y		

NOTES:

- T = Table, F = Figures, L = Listings, Y = Yes display generated, PCI = Potential Clinical Importance
- Summary = Represents Tables related to any summaries (i.e. descriptive statistics) of the observed raw data.
- Individual = Represents FL related to any displays of individual subject observed raw data.

